Potential confounders and effect modifiers

The following list presents known and potential confounders and effect modifiers in population-based IVE studies using secondary data from pre-existing databases (please also refer to DRIVE deliverable 4.1: Framework for analysis of influenza vaccine effectiveness studies).

The minimum set for a pooled analysis is marked with an asterisk (*). If available, also as many as possible of the other determinants will be harmonised between the study sites for pooled analysis according to the guidelines for harmonisation, developed according to availability of data and included in the generic study site level SAP.

- Age*
- Sex*
- Number of healthcare visits 12 months prior to the study period describing a study subject's healthcare seeking behaviour
 - (For children) Also adherence to the local childhood vaccination programme
- Chronic underlying conditions like chronic pulmonary disease, cardiovascular disease, metabolic disorders, renal disease, treatment-induced immunosuppression and disease-induced immunosuppression, medically attended obesity etc.

- (For children) Perinatal and congenital risk factors (e.g. birth weight and/or maturity at birth, perinatal factors, inborn errors of metabolism, relevant malformations and congenital syndromes)
- Number of hospitalisations 12 months prior to the study period to be used as proxy for the severity of the chronic conditions
- Pregnancy
- Influenza vaccination in previous influenza seasons; preferably more than one season,
- Pneumococcal vaccination
- Institutionalization, nursing home residence
- Contraindication to influenza vaccination
- Use of influenza antivirals
- Use of statins
- Socio-economic status or applicable proxy
- Smoking behaviour or parental smoking behaviour (for subjects ≤18 years)
- (For children) Number of siblings

➤ *Each study site to describe the factors included in the study & how these are identified.*

The list will be updated based on results of DRIVE D2.2: Systematic review of the sources of confounding, bias and strategies to manage their impact in influenza vaccine effectiveness studies, due June 2018.

Sources of information

The studies will utilize secondary data from existing population-based national, local or cohort based databases, health and social registers and/or surveillance systems by combining the information with an individual identification number, or relevant aggregation. . Examples of source databases:

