The analysis must be conducted for each exposure and outcome of interest separately. Confounder-adjusted brand-specific, type specific or overall IVE estimates will be obtained from multivariable regression models, regressing the health outcomes of interest on exposure status, age, sex and the confounders of interest. In case of effect modifiers, an interaction term between exposure and the effect modifier will be included in the regression model or stratified regression analyses will be performed.

Depending on the type of data available, the analytical method(s) will be described in the generic study site level SAP and in a study-specific SAP before the start of the study period. For the outcome of interest, irrespective of its type, multivariable logistic regression will be used, if only the number of events as vaccinated and unvaccinated by number of subjects vaccinated and unvaccinated at the end of the follow-up is known. If the number of events by person time and vaccination status can be assessed, Poisson regression will be used. In case of time-to-event data, Cox regression (proportional hazards) will be used.

Missing data

The cohort should be defined so that the missing data is minimised: the cohort should cover all subjects targeted, especially for the vaccination, and only those subjects. Especially the outcome should be caught non-differentially, i.e. similarly for vaccinated and unvaccinated (see section Study population and follow-up; Cohort of interest). Missing data for events occurring during the follow-up is not available, since 'no record' means by definition 'no event' (unless also the negative

outcome information, e.g. negative influenza tests are available, when a nested case control analysis could be performed).

Missing data may be present, if historical data for background factors at start of the follow-up is not available, e.g. if the subject has moved into the attachment area of the database recently, or it is incomplete, e.g. only part of the databases used in defining the different background factors are available. This subcohort may be excluded from the adjusted analyses.

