dement	Dementia	Numeric (Categorical)	0=No 1=Yes 9999=No information	0

stroke	History of stroke	Numeric (Categorical)	0=No 1=Yes 9999=No information	0
rheumat	Rheumatologic diseases	Numeric (Categorical)	0=No 1=Yes 9999=No information	0
obesity	Obesity	Numeric (Categorical)	0=No 1=Yes 9999=No information	0
chronic1	At least one chronic disease	Numeric (Binary)	0=No 1=Yes 9999=No information	1
chronic5	At least 5 chronic diseases	Numeric (Binary)	0=No 1=Yes 9999=No information	1
Pregnancy and perinatal/congenital risk factors (in children)				
pregnancy	Pregnancy at start of the study period	Numeric (Categorical)	0=No 1=Yes 9999=Not applicable	0
childrisk	Any perinatal or congenital risk factor in children	Numeric (Categorical)	0=No 1=Yes 9999=No information	0

Health care utilisation and propensity score				
nhosp	Number of hospitalisations 12 months prior to the study period	Numeric	≥0 or 9999=No information	2
nphcvisit	Number of outpatient primary health care visits to physician 12 months prior to the study period	Numeric	≥0 or 9999=No information	5
adherence	Adherence in the childhood vaccination program (in children)	Numeric (Categorical)	0=No 1=Low 2= Moderate 3= Complete 9999=No information	3
propensity score	Quintiles of the probability to be vaccinated according to background factors	Numeric	1-5	4
Life style, medications, social and functional status and miscellaneous				
siblings	(In children) Number of siblings living	Numeric	≥0 or 9999=No information	2
bmi	Body Mass Index	Numeric	10 to 55 or 9999=No information	22.4
smoking	Smoking status (parental smoking in children)	Numeric (Categorical)	0=Non-smoker 1=Ex-smoker 2=Smoker 9999=No information	0

dependency	Patient has contract to regular home care or difficulty in at least one category of daily living ^g	Numeric (Categorical)	0=No 1=Yes 9999=Not applicable	0
inst	Institutionalized	Numeric (Categorical)	0=No 1=Yes 9999=No information	0
contra	Contraindication for influenza vaccination	Numeric (Categorical)	0=No 1=Yes 9999=No information	0
sosstatus	Socio-economic status or applicable proxy	Numeric (Categorical)	1=low 2=medium 3= high 9999=No information	2
antiviral	Antiviral use during follow-up	Numeric (Categorical)	0=No 1=Yes 9999=No information	1
statin	Statin use during follow-up	Numeric (Categorical)	0=No 1=Yes 9999=No information	1

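### The optional antiviral covariate is an undated flag for use during follow-up; a site that adjusts for it as written conditions on a consequence of influenza and can bias VE

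*Combined protocol and SAP*

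**What the plan says.** The section on potential confounders and effect modifiers lists "Use of influenza antivirals" and "Use of statins". Only age and sex carry the asterisk of the minimum set. For the rest, the intent is: "If available, also as many as possible of the other determinants will be harmonised between the study sites for pooled analysis".

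Annex 1, under the same confounder and effect-modifier grouping, defines the two variables as "Antiviral use during follow-up" and "Statin use during follow-up". Each is coded 0, 1 or 9999. Neither has a date field or an asterisk, and antiviral use has no field separating prophylaxis from treatment.

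Under Measure of effect, adjusted estimates come from models "regressing the health outcomes of interest on exposure status, age, sex and the confounders of interest". The model depends on the data. Logistic regression is used when only end-of-follow-up counts are known. For person-time: "If the number of events by person time and vaccination status can be assessed, Poisson regression will be used". For individual times: "In case of time-to-event data, Cox regression (proportional hazards) will be used".

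Elsewhere the plan takes covariates from baseline or dates them. Annex 1 counts hospitalisations (nhosp) and primary care visits (nphcvisit) over the 12 months before the study period and takes pregnancy at its start. Pneumococcal vaccination gets a date if given during the study and a separate flag if given before. The propensity score, under Addressing confounding & bias, is built on baseline information.

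**The concern.** A confounder has to precede the outcome. Influenza antivirals are prescribed in large part because a patient has, or is thought to have, influenza, and the primary outcome is medically attended laboratory-confirmed influenza. A yes/no flag over follow-up then partly marks the case itself. No section limits it to use before the event, separates prophylaxis from treatment, or makes it time-dependent.

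In a rate or hazard model, the flagged stratum can contain so many cases that its rates approach their ceiling in both vaccine groups. The stratum rate ratio then moves toward 1 and pulls adjusted VE toward zero. In a logistic model the odds ratio survives if treatment depends on influenza alone, but not if vaccinated and unvaccinated cases are treated at different rates. The size of the bias would follow local prescribing and the model used, so it would also add heterogeneity between sites in the pooled analysis.

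**Working it through.** The plan states no figure on this point, so there is none to reproduce. As a check on the scenario values, Annex 3 formula (3) with N = 5000, coverage 50%, attack rate 5% and VE 50% gives A₁ = 62.5, A₀ = 125 and N₁ = N₀ = 2500. The lower limit is 1 − 0.5 × exp(1.96 × √0.0232) = 32.6%, in line with the claim of more than 25% under Sample size considerations.

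**Inputs.** From the plan: attack rate 5% in the unvaccinated, true VE 50%, coverage 50%. Assumed, because the documents give no prescribing figures: the share of cases and of non-cases with the flag set. There is no other confounding in the scenario.

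**Worked case: 40% of cases and 0.2% of non-cases treated, per 1,000,000 subjects.**

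| Flag | Vaccinated: cases / non-cases | Unvaccinated: cases / non-cases |
|---|---|---|
| No | 7,500 / 486,525 | 15,000 / 474,050 |
| Yes | 5,000 / 975 | 10,000 / 950 |

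1. Crude rate ratio, each subject contributing full time: (12,500/500,000) ÷ (25,000/500,000) = 0.50, so VE is 50.0%.
2. Flag = no: (7,500/494,025) ÷ (15,000/489,050) = 0.495, VE 50.5%.
3. Flag = yes: (5,000/5,975) ÷ (10,000/10,950) = 0.916, VE 8.4%.
4. A Poisson model of cases on vaccination plus flag, with log person-time as offset, forces one rate ratio on both strata. It gives 0.623, VE 37.7%.
5. Odds ratios: (7,500/486,525) ÷ (15,000/474,050) = 0.487 and (5,000/975) ÷ (10,000/950) = 0.487, equal to the crude 0.487. Logistic VE is 51.3% with or without the flag.

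**Poisson-adjusted VE over the assumed range.** In each cell the first figure gives cases full person-time (unadjusted VE 50.0%) and the second gives them half (unadjusted VE 50.6%).

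| Cases treated | 0.2% of non-cases treated | 2% of non-cases treated |
|---|---|---|
| 10% | 48.0–49.1% | 49.7–50.4% |
| 20% | 45.0–46.4% | 48.5–49.7% |
| 40% | 37.7–39.4% | 44.6–47.2% |
| 60% | 28.5–30.7% | 39.0–43.2% |

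**Cox.** A simulation of 800,000 subjects with the flag as a time-fixed covariate gave 49.2% unadjusted and 25.8% to 48.4% adjusted, with 10–60% of cases and 0.05–2% of non-cases treated.

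**Logistic, treatment depending on vaccination.** Suppose 50% of vaccinated cases, 30% of unvaccinated cases and 0.2% of non-cases are treated. The stratum odds ratios are then (6,250/486,525) ÷ (17,500/474,050) = 0.348 and (6,250/975) ÷ (7,500/950) = 0.812. The model gives VE 62.7% against 51.3% without the flag. With true VE 0%, 0.5% of non-cases treated and 30% of unvaccinated cases treated, logistic VE becomes +15.6% if 45% of vaccinated cases are treated and −13.1% if 15% are.

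**Statins.** A statin-like covariate unrelated to influenza left Poisson VE at 50.0%.

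**The case against.** The plan does not commit to this adjustment. The variable has no asterisk, the list covers effect modifiers as well as confounders, and the regression text refers only to the confounders of interest. Annex 2, not yet written, is to define and harmonise the variables and update Annex 1; the confounder list awaits a systematic review; and each site must describe its own factors. This stands. A reader might infer that every adjusted estimate in the project will carry the bias, and the documents do not support that: harm needs a later choice by a site or by Annex 2. The stated wish to harmonise as many determinants as possible makes that choice plausible, no more.

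Under Individual follow-up, a subject's follow-up ends at the first outcome, so use during follow-up could be read as excluding later treatment. A site with dated prescription or dispensing records could apply that reading when it builds the flag. This stands in part. Nothing instructs sites to do so, an undated flag cannot be checked once submitted, and treatment on or before the sampling date would still count.

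The size depends on non-case use. In the worked case 15,000 of 16,925 flagged subjects (89%) are cases. With 2% of non-cases treated, the share is 15,000 of 34,250 (44%) and the bias shrinks. The Background says laboratory confirmation captures only a minor part of the burden, and sampling is usually clinician-driven, so treated but untested patients would count as non-cases. This stands: that the flagged stratum is mostly cases is an assumption.

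The propensity score rests on baseline information, so it would already leave this flag out. That is true, but it does not cover direct entry of the flag in the regression.

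**Conclusion.** The point holds for antivirals, conditionally. As defined, the flag can be a consequence of the outcome, and a site that adjusts for it can get a biased VE. In the plan's own scenario with true VE 50%, Poisson-adjusted VE runs from about 29% to 50%, depending on assumed treatment of 10–60% of cases and 0.2–2% of non-cases. Where few cases are treated, the loss is at most about two points. Logistic VE is untouched if treatment is independent of vaccination and moves in either direction otherwise. The premise that antivirals are largely given because of influenza is subject knowledge.

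Two stronger readings are not supported. A reader might infer that adjusting always does worse than the crude estimate. That does not follow: the logistic result can be unchanged, and the scenarios contain no other confounding for adjustment to remove. A reader might also infer that the statin flag distorts VE in the same way. There is no outcome-driven mechanism for statins and no bias was shown; what remains is a minor inconsistency of timing with the plan's baseline covariates.

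Severity: should-fix, conditional on a site using the variable.

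**What to change.** In the confounder list and in Annex 1, state that antiviral use during follow-up is not part of the VE adjustment set. If prophylactic use is thought to matter, replace the flag with dispensing dates and admit only use before the event and not for the current illness, as a time-varying covariate. Carry the same rule into Annex 2 when it is written.

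For consistency only, define statin use over the 12 months before the study period, as is done for nhosp and nphcvisit.

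The cost is two variable definitions in Annex 1 and one line in the confounder list. Prescription and pharmacy-delivery registers are already among the example sources. The dated option needs those registers to hold dates; excluding the flag needs no new data. The change is cheapest before sites adapt the protocol from season 2018/19.

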Annex 2: Generic study site level Statistical Analysis Plan (SAP)

After analysing the characteristics and structure of the databases used by the participating study sites, a generic study site level statistical analysis plan (SAP) will be developed, including instructions and/or alternatives for defining and harmonising the study variables, including those used for adjusting for potential confounders and effect modifiers, like chronic conditions.

This study site level SAP will be updated annually before the start of the study period, according to experience of the collaboration, to availability of data in participating study sites, and perhaps to predicted features of the upcoming epidemic. This study site level SAP will also be used for updating the Study dataset (Annex 1), if needed.

Annex 3: Sample size considerations for cohort studies

Authors: [name] and [name]

For questions or feedback, please contact

e-mail: [contact]

This document provides sample size estimations for estimating overall and brand-specific influenza vaccine effectiveness (VE) using the cohort design. The minimal detectable VE as well as precision estimates are provided for various parameter settings and recommendations are formulated.

Minimal detectable vaccine effectiveness

The minimal detectable VE is the smallest VE that can be detected as significantly greater than zero in a given study using hypothesis testing. The minimal detectable VE for a cohort study is estimated as

$$VE_{MD} = 1 - RR_{MD(RR<1)}, \quad (1)$$

where $RR_{MD(RR<1)}$ is the minimal detectable relative risk (RR) if $RR < 1$, or

$$RR_{MD(RR<1)} \cong \frac{1}{2a} \left(b - \sqrt{b^2 - 4ac} \right), \quad (2)$$

where

$$a = Y + \pi Z; \quad b = 2Y + Z; \quad c = Y - r(1 - \pi)Z,$$

in which

$$Y = rN\pi^2; \quad Z = (r + 1)\pi \left(z_{\frac{\alpha}{2}} + z_{\beta} \right)^2$$

for attack rate in the unexposed π , exposed to unexposed ratio r with $r = \gamma/(1 - \gamma)$ with coverage γ , total sample size N , and where z_{α} and z_{β} are the standard normal z-score for the type I and type II error rates (Woodward 2013).

We calculated the minimal detectable overall VE (1) with 80% power ($1 - \beta$) and a two-sided 95% confidence coefficient ($1 - \alpha/2$) for cohort studies with the total number of subjects varying from 1000 to 50000, while assuming overall vaccination coverages of 5%, 20%, 50% and 70% and an attack rate of 5% and 15% in the unvaccinated.

We additionally calculated the minimal detectable brand-specific VE, where subjects are considered exposed when they were vaccinated with the brand of interest and unexposed when they were unvaccinated during the study's follow-up. This means that the same comparator group of unexposed subjects is used for the different brand-specific estimates. The minimal detectable brand-specific VE is calculated for the same settings above, additionally assuming that the brand of interest accounts for 10%, 20%, 40%, 60%, 80% and 90% of the overall vaccination coverage.

The results for the minimal detectable overall VE are given in Figure 1. These figures represent the minimal detectable VE by total sample size. The results for the minimal detectable brand-specific VE for 5% and 15% attack rates in the unvaccinated are given in Figure 2 and Figure 3, respectively.

[figure not shown]

Figure 1. Minimal detectable overall VE for a cohort study assuming vaccination coverage of 5%, 20%, 50% and 70%, and 5% and 15% attack rate in the unvaccinated, by total sample size.

[figure not shown]
[figure not shown]
[figure not shown]

[figure not shown]
Figure 2. Minimal detectable brand-specific VE for a cohort study assuming 5%, 20%, 50% and 70% overall vaccination coverage with the brand of interest covering 10%, 20%, 40%, 60%, 80% and 90% of the overall coverage and 5% attack rate in the unvaccinated, by total sample size.

[figure not shown]
a) 5% overall coverage

b) 20% overall coverage

c) 50% overall coverage

d) 70% overall coverage

Figure 3. Minimal detectable brand-specific VE for a cohort study assuming 5%, 20%, 50% and 70% overall vaccination coverage with the brand of interest covering 10%, 20%, 40%, 60%, 80% and 90% of the overall coverage and 15% attack rate in the unvaccinated, by total sample size.

Precision

The precision refers to the level of sampling error. The standard error and consequently the width of confidence intervals (CI) are measures of precision. As the VE CI are asymmetric, we express precision as the lower limit of the two-sided CI of the anticipated true VE, expressed in %.

For a cohort study, the precision can be derived starting from the anticipated true VE, the confidence coefficient ($1 - \alpha/2$), the total sample size N, the attack rate AR in the unvaccinated and the overall vaccination coverage γ .

Then, from the lower limit of the CI for VE based on cohort studies, or

$$VE_{LL\ CI} = 1 - \exp \left[\log(RR) + Z_{\alpha/2} \sqrt{\frac{1}{A_1} - \frac{1}{N_1} + \frac{1}{A_0} - \frac{1}{N_0}} \right], \quad (3)$$

where $RR = 1 - VE$, $Z_{\alpha/2}$ is the standard normal z-score, A_1 and A_0 are the number of exposed and unexposed cases and where N_1 and N_0 are the number of exposed and unexposed subjects, it follows that the precision is determined for given values A_1 , A_0 , N_1 and N_0 .

The values for A_1 , A_0 , N_1 and N_0 can be derived from the sample size N, the attack rate AR and the overall vaccination coverage γ , or

$$A_1 = N * \gamma * AR * (1 - VE)$$

[figure not shown]
$$A_0 = N * (1 - \gamma) * AR$$

$$N_1 = N * \gamma$$

[figure not shown]
$$N_0 = N * (1 - \gamma)$$

We calculated precision of the overall VE based on a two-sided 95% CI for cohort studies with the total number of subjects varying from 1000 to 50000, whilst assuming overall vaccination coverages of 5%, 20%, 50% and 70%, VE of 20%, 50% and 70%, and an attack rate in the unvaccinated of 5% and 15%. To calculate the precision of the brand-specific VE, we additionally assumed that the brand of interest accounts for 10%, 20%, 40%, 60%, 80% and 90% of the overall vaccination coverage

[figure not shown]
The results for precision of the overall VE assuming attack rates in the unvaccinated of 5% and 15% are given in Figures 4 and 5, respectively. These figures represent precision by total sample size. The results for the precision of brand-specific VE for anticipated true VE of 20%, 50% and 70%, and 5% attack rate are given in Figures 6 to 8.

a) 20% VE

b) 50% VE

c) 70% VE

Figure 4. Precision of overall VE for a cohort study assuming vaccination coverage of 5%, 20%, 50% and 70%, VE of 20%, 50% and 70% (indicated with the black horizontal line), and 5% attack rate in the unvaccinated, by total sample size.

[figure not shown]
[figure not shown]
[figure not shown]

[figure not shown]
Figure 5. Precision of overall VE for a cohort study assuming vaccination coverage of 5%, 20%, 50% and 70%, VE of 20%, 50% and 70% (indicated with the black horizontal line), and 15% attack rate in the unvaccinated, by total sample size.

[figure not shown]
a) 5% overall coverage

b) 20% overall coverage

[figure not shown]

c) 50% overall coverage

[figure not shown]

d) 70% overall coverage

[figure not shown]
Figure 6. Precision of brand-specific VE for a cohort study assuming an anticipated true VE of 20% (indicated with the black horizontal line), overall vaccination coverage of 5%, 20%, 50% and 70% with the brand of interest covering 10%, 20%, 40%, 60%, 80% and 90% of the overall coverage, and 5% attack rate in the unvaccinated, by total sample size.

[figure not shown]
a) 5% overall coverage

b) 20% overall coverage

[figure not shown]

c) 50% overall coverage

[figure not shown]

d) 70% overall coverage

[figure not shown]
Figure 7. Precision of brand-specific VE for a cohort study assuming an anticipated true VE of 50% (indicated with the black horizontal line), overall vaccination coverage of 5%, 20%, 50% and 70% with the brand of interest covering 10%, 20%, 40%, 60%, 80% and 90% of the overall coverage, and 5% attack rate in the unvaccinated, by total sample size.

[figure not shown]
a) 5% overall coverage

b) 20% overall coverage

c) 50% overall coverage

d) 70% overall coverage

Figure 8. Precision of brand-specific VE for a cohort study assuming an anticipated true VE of 70% (indicated with the black horizontal line), overall vaccination coverage of 5%, 20%, 50% and 70% with the brand of interest covering 10%, 20%, 40%, 60%, 80% and 90% of the overall coverage, and 5% attack rate in the unvaccinated, by total sample size.

Concluding remarks and recommendations

We make the following observations and recommendations based on our sample size calculations for single-site cohort studies;

- We recommend cohort studies based on 5000 subjects or more. A cohort study with 5000 subjects will result in a minimal detectable overall VE of 30-40% for an influenza attack rate of 5% and coverages >20%.
- A cohort study based on 5000 subjects will result in minimal detectable brand-specific VE of 30-40%, for an influenza attack rate of 5% and brands covering 40% to 90% of the influenza vaccines when the overall vaccination coverage is 50% or more.
- A cohort study with a total sample size of 20.000 will result in a minimal detectable VE of 18-20% for an influenza attack rate of 5% and overall vaccination coverages of 20% or more. Improvements in accuracy both in terms of minimal detectable VE and precision will be minimal when increasing sample sizes further.
- In case higher influenza attack rates (+15%) would be expected, lower sample sizes are needed to obtain VE estimates with acceptable precision.
- In case the VE is expected to be low (< 20%), higher sample sizes are required to obtain VE estimates with acceptable precision.
- In case interest is in VE within subgroups, the sample size calculations should be done with respect to the subgroup-specific sample size.
- **IMPORTANT:** These are recommendations to support the design of cohort studies on (brand-specific) influenza VE. Obtaining a minimum sample size is not a requirement for study participation.

References

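### The Annex 3 sample-size figures describe a crude comparison, are not labelled so, and are somewhat optimistic for the confounder-adjusted VE that the protocol plans

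*Combined protocol and SAP*

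**What the plan says.** Annex 3 sets out two calculations for single-site cohorts.

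- *Minimal detectable VE.* "We calculated the minimal detectable overall VE (1) with 80% power" and "a two-sided 95% confidence coefficient", for "an attack rate of 5% and 15% in the unvaccinated". Formula (2) takes the attack rate, the exposed-to-unexposed ratio, N and two z-scores.
- *Precision.* Formula (3) takes exposed and unexposed cases and subjects. These "can be derived from the sample size N, the attack rate AR and the overall vaccination coverage", plus the assumed VE.

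The concluding remarks of Annex 3 state: "We recommend cohort studies based on 5000 subjects or more". Such a cohort "will result in a minimal detectable overall VE of 30-40% for an influenza attack rate of 5% and coverages >20" per cent. They give the same 30-40% for brand-specific VE when the brand has 40% to 90% of the vaccines and overall coverage is at least 50%, and 18-20% for 20,000 subjects. The main text (Sample size considerations) adds that 5000 subjects give a lower 95% limit above 25% at a true VE of 50%. It says this for overall VE at coverage above 20%, and for brand-specific VE under the brand conditions just given.

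Under Measure of effect, a crude VE is defined first. Then: "Confounder-adjusted brand-specific, type specific or overall IVE estimates will be obtained from multivariable regression models", with age, sex and the confounders of interest as regressors. Under Potential confounders and effect modifiers, "The minimum set for a pooled analysis is marked with an asterisk"; age and sex carry it. Addressing confounding & bias mentions propensity-score quintiles as one possible adjustment.

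**The concern.** A covariate that predicts vaccination leaves less independent variation in vaccination from which to estimate its effect. For a rare outcome, the variance of the adjusted log RR is roughly 1/(1-R2) times the crude variance. Age is in the compulsory set and vaccination is recommended by target group, so R2 will not be zero. Other listed covariates, such as vaccination in earlier seasons and chronic conditions, can raise it further. At a 5% attack rate, covariates that predict the outcome give almost no precision back.

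Neither formula allows for this, no other section does, and nothing labels the results as crude. Sites are told to use them for design. A site could therefore expect its adjusted VE to be as precise as the unadjusted one. Pooling does not remove this, because each site's adjusted variance carries into the pooled estimate.

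**Working it through.** **Inputs.** From Annex 3: N = 5000, attack rate 5%, 80% power, two-sided 95%, coverage 20, 50 and 70%. The precision figures use a true VE of 50%. Brand share 40% is the lower end of the range in the stated brand claim. I use 21% coverage for just above 20%. R2 of 0.1, 0.2 and 0.3 is my assumption.

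**Step 1: reproduce the plan's figures (crude).**

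Formula (2) at 50% coverage: r = 1; Y = 5000 × 0.05² = 12.5; Z = 2 × 0.05 × (1.960 + 0.842)² = 0.785; a = 12.539; b = 25.785; c = 12.5 − 0.95 × 0.785 = 11.754. RR = (25.785 − √(25.785² − 4 × 12.539 × 11.754)) / (2 × 12.539) = 0.682, so VE = 31.8%. At 20% and 70% coverage it gives 36.6% and 35.7%. All lie within the stated 30-40%.

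Formula (3) at 21% coverage: N1 = 1050, N0 = 3950, A1 = 26.25, A0 = 197.5. Variance = 1/26.25 − 1/1050 + 1/197.5 − 1/3950 = 0.0420; SE = 0.2048. Lower limit = 1 − 0.5 × exp(1.96 × 0.2048) = 25.3%, as stated.

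Formula (3) for a 40% brand at 50% coverage: N1 = 1000, N0 = 2500, A1 = 25, A0 = 125. Variance = 0.0400 − 0.0010 + 0.0080 − 0.0004 = 0.0466; SE = 0.2159. Lower limit = 23.7%, already below the stated 25% without any adjustment.

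**Step 2: inflate.** Multiply the variance in (3) by 1/(1−R2), that is 1.11, 1.25 and 1.43. Multiply N in (2) by (1−R2). Example, 21% coverage and R2 = 0.2: variance 0.0420 × 1.25 = 0.0524, SE 0.2290, lower limit 21.7%.

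| N = 5000, attack rate 5% | Stated | Crude | R2 0.1 | R2 0.2 | R2 0.3 |
|---|---|---|---|---|---|
| Minimal detectable overall VE, coverage 21% | 30-40% | 36.1 | 37.7 | 39.6 | 41.8 |
| Same, coverage 50% | 30-40% | 31.8 | 33.4 | 35.2 | 37.4 |
| Same, coverage 70% | 30-40% | 35.7 | 37.5 | 39.6 | 42.2 |
| Minimal detectable brand VE, coverage 50%, share 40% | 30-40% | 39.0 | 40.8 | 42.8 | 45.2 |
| Lower limit, overall, coverage 21% | >25% | 25.3 | 23.7 | 21.7 | 19.2 |
| Lower limit, overall, coverage 50% | >25% | 32.6 | 31.5 | 30.2 | 28.6 |
| Lower limit, brand, coverage 50%, share 40% | >25% | 23.7 | 21.9 | 19.8 | 17.1 |

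With 20,000 subjects, minimal detectable VE at coverage 20, 50 and 70% is 19.9, 16.6 and 18.3% crude, and 22.0, 18.4 and 20.4% at R2 = 0.2 (stated: 18-20%).

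**Step 3: where the stated figures break.** For the lower limit at 21% coverage to equal 25%, the SE must be ln(0.75/0.5)/1.96 = 0.2069. The variance ratio is 0.2069²/0.2048² = 1.02, so R2 is about 0.02. The 40% brand at 50% coverage passes 40% at R2 of about 0.06. Overall minimal detectable VE passes 40% at R2 of about 0.22 (coverage 21%), 0.40 (50%) and 0.22 (70%).

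**Step 4: how good is 1/(1−R2)?** Take age in two strata with equal attack rates: 20% elderly at 60% coverage, the rest at 10%. Overall coverage is 20%, and R2 = (0.2 × 0.4² + 0.8 × 0.1²)/(0.2 × 0.8) = 0.25. The approximation gives 1/0.75 = 1.33; combining the stratum log RRs by inverse variance gives 1.23. The direction agrees and the size is approximate.

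**The case against.** **Nothing is miscalculated.** This stands. Annex 3 lists its inputs openly and its formulas reproduce the 5000-subject range for overall minimal detectable VE. A crude VE is planned too, and for it the figures apply as they are. The documents never name the adjusted estimate as primary. A reader might infer that the sample-size arithmetic is wrong, or that the plan rests on adjusted VE alone; the text supports neither.

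**The 30-40% range mostly survives.** This also stands, up to R2 of about 0.2. One could calculate that power at a VE of 36.6% (20% coverage) falls from 80% to 76, 71 or 65% at R2 of 0.1, 0.2 or 0.3, and call that a failure of a stated figure. But 36.6% is derived from formula (2); the documents state only the range. Likewise, a lower limit under 25% at exactly 20% coverage contradicts nothing, since the claim is for coverage above 20%.

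**The direction could reverse.** In the two-strata example, let the elderly attack rate be twice that of the others, keeping 5% among the unvaccinated overall. The adjusted variance is then 0.90 times the Annex 3 value. But this comes from more vaccinated cases: the attack rates become 9.09% and 4.55%, so the vaccinated cases are 600 × 0.0909 × 0.5 + 400 × 0.0455 × 0.5 = 36.4, against the 25 that Annex 3 assumes. Against a crude analysis of the same data the factor is 1.26. For elderly-to-other ratios from 0.5 to 2 it runs from 1.16 to 1.26. So adjustment widens the interval, although the gap from the printed figures also depends on stratum attack rates that the documents do not give.

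**Little hangs on 5000.** Mostly right. It is a recommendation and not a condition of participation, a single study may not be powered alone, and data are pooled. This limits the weight of the point. It does not make the unlabelled figures apply to the adjusted VE.

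**Conclusion.** The point holds as a matter of labelling and mild optimism. The figures in Annex 3, and those in the main text, are for a crude comparison and do not say so. For the adjusted VE, the broad overall statements mostly hold at R2 up to about 0.2. The statements with little margin do not: the lower limit just above 20% coverage, and the brand-specific figures at a 40% share. Brand-specific VE comes first in the primary objective, so the latter matter most. That brand's lower limit misses the stated 25% even before adjustment.

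The size rests on an assumed R2 and on an approximation for a rare outcome with similar attack rates across covariate strata. A reader might conclude that 5000 subjects are too few or that recruitment must grow. The documents do not support that: they set no minimum size and rely on pooling.

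**What to change.** 1. Label the present figures in Annex 3 and in Sample size considerations as crude, unadjusted.
2. Add a sensitivity table to Annex 3 for R2 of 0.1, 0.2 and 0.3, or a site's own value from prior-season data. Multiply the variance under the root in formula (3) by 1/(1−R2) and multiply N in formula (2) by (1−R2). Define R2 as that of vaccination on the planned adjustment set. State that this is an approximation, with the assumptions given above.
3. Qualify the 5000- and 20,000-subject statements in both places, and correct the brand-specific lower-limit statement at the 40% share.

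The cost is a recalculation and some wording. No subjects or data are added and the recommended cohort size can stay. The stated figures become slightly less favourable.
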